### **Treatment Period - Phase II**

Phase II is a multicentre study with open-label multiple single arm cohorts using Simon's optimal two-stage design to evaluate the efficacy, as assessed by ORR, of treatment with  $^{177}\text{Lu}$ -OPS201 in subjects with locally advanced or metastatic SCLC, or metastatic HR+/HER2- BC expressing sstr2, as identified by  $^{68}\text{Ga}$ -OPS202 PET/CT scans.

Approximately 76 subjects with locally advanced or metastatic SCLC and approximately 96 subjects with metastatic HR+/HER2- BC deemed sstr2-positive on  $^{68}\text{Ga}$ -OPS202 PET/CT scans will receive the  $^{177}\text{Lu}$ -OPS201 treatment regimen recommended based on the results of the phase I. It is expected that two cycles of  $^{177}\text{Lu}$ -OPS201 will be administered in subjects enrolled in phase II.

For phase I and phase II studies, up to four additional cycles might be administered in subjects who tolerate the treatment well and show clinical benefit (CR, PR, or stable disease) after the first two cycles.

These additional cycles will be administered at radioactivity adjusted based on dosimetry results, provided limiting organ radiation dose levels have not been exceeded.

Additional cohorts could be added to the study according to evidence based on preclinical and clinical work and data on  $^{68}\text{Ga}$ -OPS202 and  $^{177}\text{Lu}$ -OPS201, sstr2 expression and candidate diseases.

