### **1.2.2 Study exposure**

In phase I, for subjects receiving only two treatment cycles of  $^{177}\text{Lu}$ -OPS201, this study will consist of up to 3-week screening period and a 12-week dosing period (+ up to additional 4 weeks in case of adverse events (AEs) that need to be adequately recovered). A treatment cycle is defined as the timeframe of 6 (up to 10) weeks between two administrations or the timeframe of 6 weeks following the last administration. In case of logistical issues, the cycle could be extended by up to additional 2 weeks. Dosing period can be extended up to 36 weeks in case subjects receive up to four additional cycles. Subjects are thus expected to participate in this study for a minimum of 15 weeks and up to 39 weeks (+ up to additional 4 weeks in case of AEs that need to be adequately recovered). In all cases, a long-term follow-up lasting 24 months will start after the end of the last  $^{177}\text{Lu}$ -OPS201 cycle.

For phase II, it is anticipated that the duration of the study will be identical to the duration in phase I; however, pending the results of phase I on recommended treatment regimen (doses and intervals) the study duration will be refined.

The subject's participation in the treatment period of the study will be considered to have ended at the end of core trial (EOCT) or end of additional cycles (EOAC) visit. The subject's participation in the 24-month follow-up period of the study will be considered to have ended when the subject dies, withdraws consent to the follow-up period, or ends the 24-month follow-up, whichever occurs first.

The overall duration of the study will be approximately 5.5 years. The study will be considered to have started when the first site has been initiated.

The study will be considered to have ended after the last subject has completed the last follow-up visit in the study.

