**Table 2 Primary and Secondary Tumour Activity Endpoints and Evaluations**

Measure	Timepoint	Variable	Endpoint
Tumour size (longest diameter)	Screening [a] and 6 weeks after each $^{177}\text{Lu}$ -OPS201 administration (each cycle)	Tumour response according to RECIST v1.1	
 
ORR
 
BOR
 
PFS (complemented with events of death)
 
DRR (CR or PR lasting <math>\geq 6</math> months)
 
DCR
 
TTP
 
TTR
 
DoR
 

Tumour size (longest diameter)	Screening [a] and 6 weeks after second $^{177}\text{Lu}$ -OPS201 administration (second cycle)	Tumour response according to mGa-RECIST; Metabolic tumour response by $^{18}\text{F}$ -FDG-PET – PERCIST v1.0 and $^{68}\text{Ga}$ -OPS202 by mGa-PERCIST*	
 
ORR
 
BOR
 

Tumour volume	Screening [a] and 6 weeks after each $^{177}\text{Lu}$ -OPS201 administration (each cycle)	Mean change (%) in tumour volume assessed by volumetric CT/MRI	% change from baseline in tumour volume
Event of death	1 and 2 years	Death count	OS
$\text{SUV}_{\max}$ and $\text{SUV}_{\text{mean}}$	Screening [a] and 6 weeks after second $^{177}\text{Lu}$ -OPS201 administration (second cycle)	sstr2 targeted tumour uptake by $^{68}\text{Ga}$ -OPS202- PET/CT	Change in tumour uptake on $^{68}\text{Ga}$ -OPS202 PET/CT scan

Measure	Timepoint	Variable	Endpoint
SUL max and SUL mean	Screening [a] and 6 weeks after second  Lu-OPS201 administration (second cycle)	Tumour-to-background ratio by  F-FDG-PET using PERCIST v1.0	Quantitative changes in tumour-to-background  F-FDG-PET uptake
SUV max and SUV mean	Screening [a] and 6 weeks after second  Lu-OPS201 administration (second cycle)	 Ga-OPS202 uptake and  Lu-OPS201 therapy response	Change in  Ga-OPS202 uptake on PET scan in subjects screened for  Lu-OPS201 treatment as compared to clinical response and ORR

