## **Phase II**

Phase II primary endpoint is to evaluate the ORR of fractionated i.v. administration of  $^{177}\text{Lu}$ -OPS201 in previously treated subjects with locally advanced or metastatic cancers expressing sstr2 as identified by  $^{68}\text{Ga}$ -OPS202 PET/CT scans. The primary endpoint is ORR measure by RECIST 1.1 over the two treatment cycles of the core study. Objective response is defined as the sum of PR and CR measured by CT or MRI using RECIST version 1.1. Tumour response assessments are performed 6 weeks after each administration of  $^{177}\text{Lu}$ -OPS201 during the core study or at the time of occurrence of first clinical signs of disease progression as determined by the investigator. All images will be sent to an ICL for evaluation and confirmation of response.

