## **Phase II**

### **Efficacy**

- Durable response rate (DRR: CR or PR lasting  $\geq 6$  months)
- Progression free survival (PFS) as determined from start of study treatment until occurrence of tumour progression or death. Progression will be radiologically assessed by RECIST v1.1 and “mGa-RECIST” as two separate endpoints; for RECIST it will be measured at Screening and 6 weeks after each  $^{177}Lu$ -OPS201 administration (each cycle); for “mGa-RECIST” it will be measured at Screening and 6 weeks after the second  $^{177}Lu$ -OPS201 administration (second cycle).

PFS (months) = (event or censoring date – first dose date + 1)/30.4375

PFS will be right-censored for subjects who met one or more of the following conditions:

- no baseline disease assessment or no evaluable post baseline disease assessments unless death occurred prior to the first planned assessment at post baseline (in which case death will be considered a PFS event).

SAP Final: Version 2.0: [03 January 2020]

32/57

- amputation or surgical resection of tumour in the absence of documented disease progression.
- subsequent anticancer therapy in the absence of documented disease progression.
- died or documented disease progression after missing two or more consecutively scheduled disease assessment visits
- alive and without documented disease progression on or before the data cutoff date

If a subject meets more than one of these conditions, then the scenario that occurs first will be used for analysis. The progression or censoring date will be determined based on the conventions listed in Table 4:

Table 4 Date of Progression or Censoring for PFS

Situation	Date of progression or censoring	Outcome
Death before first planned disease assessment	Date of death	Event
Death or disease progression between planned disease assessments	Date of death or first disease assessment showing disease progression, whichever occurs first	Event
No baseline disease assessment or no evaluable post-baseline disease assessments	Date of first dose of  Lu-OPS201	Censored
Surgical resection or subsequent anticancer treatment started before disease progression or death (without disease progression beforehand)	Date of last disease assessment prior to surgery or start of subsequent anticancer treatment	Censored

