## **Phase II**

- ORR over the two treatment cycles of the core study measured by the ICL. Objective response is defined as the sum of PR and CR measured by CT or MRI using RECIST version 1.1. Tumour response assessments are performed 6 weeks after each administration of Lu-OPS201 during the core study or at the time of occurrence of first clinical signs of disease progression as determined by the investigator. The point estimates of the ORR will be calculated and accompanied by a 95% exact binomial confidence interval (CI) using the Clopper-Pearson method. ORR by Ga-OPS202 PET mGa-RECIST, will also be analysed similarly. ORR of CMR and PMR by PERCIST 1.0 and by mGa-PERCIST will be analysed similarly as ORR by RECIST 1.1.
- The summaries of BOR will include number and percentage of subjects in each of these categories (CR, PR, SD, PD, NE, NA). BOR will be assessed based on RECIST v1.1 ([Eisenhauer EA, 2009](#)). BOR by Ga-OPS202 mGa-RECIST will also be analysed similarly. BOR by F-FDG-PET PERCIST v1.0 and by mGa-PERCIST will be analysed similarly as BOR by RECIST 1.1 using each of these categories (CMR, PMR, SMD, PMD, NE, NA).
- DRR by RECIST v1.1 defined as the percentage of subjects who have achieved a response of CR, PR or stable disease, will be analysed and summarised in the same manner as ORR.
- PFS by RECIST v1.1 will be summarised descriptively using the Kaplan-Meier method. The Kaplan-Meier estimates of the median PFS, and the corresponding 2-sided 95% confidence intervals calculated using Greenwood's formula will be presented.

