- OS is defined as the time from the date of first dose of  $^{177}\text{Lu}$ -OPS201 to the date of death due to any cause. Subjects who have not died will be censored at the date of last contact which may be identified from a visit date or any study assessment (physical examination, vital signs, ECOG performance status, ECG, study drug record, radiological evaluation, laboratory sampling, concomitant or follow-up procedures), AE, medication, or disposition information. OS will be calculated using the Kaplan-Meier method. One-year and two-year survival are defined as the subject survival probability at 1 year and 2 years, respectively, after the date of first dose of  $^{177}\text{Lu}$ -OPS201. One-year and two-year survival probability along with the associated 2-sided 95% confidence intervals, will be provided. If there are a sufficient number of OS events (i.e., deaths), median OS time, first and third quartiles and associated 95% 2-sided confidence intervals, will be estimated using the Brookmeyer-Crowley method ([Brookmeyer, 1982](#)). Kaplan-Meier OS curves also will be provided.
- DCR by RECIST v1.1, defined as the percentage of subjects who have achieved a response of CR, PR or stable disease, will be analysed and summarised in the same manner as ORR.
- TTP by RECIST v1.1, defined as the time from date of first dose of  $^{177}\text{Lu}$ -OPS201 to the date of first documentation disease progression as determined by the investigator, will be analysed and summarised in the same manner as PFS.
- TTR by RECIST v1.1, defined as the time from the date of first dose of  $^{177}\text{Lu}$ -OPS201 to the date of the first documentation of a response (CR or PR whichever occurs first) in a subject who responded, will be analysed and summarised in the same manner as PFS.
- DoR by RECIST v1.1, defined as the time from date of first documentation of response (CR or PR whichever occurs first) to the date of disease progression or to death due to any cause, whichever occurs first, will be analysed and summarised in the same manner as PFS.

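### The Phase II analysis text gives durable response rate (DRR) the disease control rate (DCR) definition, against the SAP's own definition of CR or PR lasting at least 6 months

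*SAP*

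**What the plan says.** The abbreviation list expands DRR as durable response rate. The SAP then defines it in three places.

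- Table 2 (section 1.3.2.1, Phase II) lists "DRR (CR or PR lasting" at least 6 months, with DCR as a separate entry.
- Section 3.1.2, Phase II efficacy, opens its list with "Durable response rate (DRR: CR or PR lasting" at least 6 months. DCR again appears separately, among the other response endpoints.
- Section 3.2.1.1, Phase II, which says how each endpoint is analysed, has "DRR by RECIST v1.1 defined as the percentage of subjects who have achieved a response of CR, PR or stable disease", and refers to ORR for the method.

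Further down the same Phase II list stands "DCR by RECIST v1.1, defined as the percentage of subjects who have achieved a response of CR, PR or stable disease", with the same reference to ORR.

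**The concern.** The analysis bullet departs from the endpoint definition in two ways: it counts stable disease as a success, and it drops the duration condition that gives the endpoint its name. The two definitions cannot both be programmed. A programmer works from the analysis section, so the text as it stands would put disease control under a durable-response label. A reader of such a table would take subjects with stable disease, and subjects whose response was brief, for durable responders. The proportion that Table 2 and section 3.1.2 promise would appear nowhere.

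**Working it through.** No figure in the SAP belongs to this point, so the check compares the definitions and then works out what separates them.

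**Step 1. Definitions side by side**

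| Place in the SAP | Endpoint | Responses counted | Duration condition |
|---|---|---|---|
| Table 2 | DRR | CR, PR | at least 6 months |
| 3.1.2, Phase II | DRR | CR, PR | at least 6 months |
| 3.2.1.1, Phase II | DRR | CR, PR, stable disease | none |
| 3.2.1.1, Phase II | DCR | CR, PR, stable disease | none |
| 3.2.1.1, Phase I | DCR | CR, PR, stable disease | none |
| 3.1.2, Phase I | DCR | CR, PR, stable disease | none |
| 1.3.2.1, RECIST v1.1 text for Phase I | DCR | CR, PR, stable disease | none |

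The third row is the only place that attaches stable disease to DRR. Its wording matches the Phase II DCR bullet apart from a comma. It matches the Phase I DCR bullet apart from the abbreviation, and like that bullet it stands directly before PFS. This looks like a copied DCR sentence with the label changed, not a deliberate second definition.

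**Step 2. What separates the two figures**

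Take one assessment window and one denominator N. Let S be the subjects whose best response is stable disease, R the subjects with CR or PR, and L those of the R whose response lasts at least 6 months.

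- Figure as written = (R + S)/N, which is DCR.
- Intended DRR = L/N.
- Difference = (S + R − L)/N, the share with stable disease as best response or with a response shorter than 6 months.

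The difference is never negative. It is zero only if no subject has stable disease as best response and every response lasts 6 months. For scale, at the planned response-evaluable numbers in section 1.3.4, each such subject adds 1/69 = 1.4 percentage points in the SCLC cohort or 1/87 = 1.1 points in the BC cohort. The ITT denominators could differ. The SAP states neither a stable-disease rate nor a response-duration distribution, so S and R − L cannot be filled in.

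The common window matters. Section 1.2 allows up to four additional cycles in subjects with stable disease after the first two, so a response may first appear after the core study. If the two figures were taken over different windows, this decomposition would not apply exactly.

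**Step 3. Does another analysis supply the missing endpoint?**

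DoR (section 3.1.2, Table 6, and section 3.2.1.1) is a time-to-event summary among responders only. It does not give the proportion of all analysed subjects with a response of at least 6 months.

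**Step 4. What is not touched**

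The primary endpoint and the two-stage rules in sections 1.3.4 and 3.2.16 depend on ORR alone. DRR enters neither.

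**The case against.** The strongest counter-argument is section 5. Because the study closed prematurely, the study report was cut to selected listings: disposition, deviations, demographics, product administration and adverse events. None is an efficacy output, so the duplicated DCR will not appear in the report now planned. This stands, and it makes the correction largely editorial for that report. It does not make the Phase II text right. Section 3.2.1.1 remains in the final version 2.0, and anyone programming from it or reusing it would meet the wrong rule.

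It can also be said that the intent is plain, since two other places agree on the 6-month definition. That is true. It makes the repair safe, but the contradiction remains in the one section that directs the analysis.

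A reader might go further and infer that DRR has no workable window. The bullet sends DRR to the ORR method, and for ORR the SAP says "The primary endpoint is ORR measure by RECIST 1.1 over the two treatment cycles of the core study". With "this study will consist of up to 3-week screening period and a 12-week dosing period" in Phase I, a response lasting 6 months would not fit. The document does not support this reading:

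- Section 3.2.1.1 uses the same cross-reference to ORR for the baseline proportion of sstr2-positive subjects, which cannot inherit a post-treatment window.
- The same section refers DoR to the PFS method although the two have different starting points. Such references carry over the estimator and its interval, not the assessment period.
- The two-cycle limit is stated for ORR only.
- Follow-up runs for 2 years after the last cycle (section 1.2), and PFS is evaluated up to 2 years after the end of the core trial (section 1.1.2).
- The Phase II timetable is not fixed: "For phase II, it is anticipated that the duration of the study will be identical to the duration in phase I", to be refined after Phase I.

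**Conclusion.** The definition error is confirmed, and its severity is minor. The Phase II analysis bullet for DRR states DCR, contradicts Table 2 and section 3.1.2, and leaves the stated 6-month endpoint without an analysis. Its size is the share of subjects with stable disease as best response or a response under 6 months. That expression assumes a common window and denominator, and the SAP offers nothing from which to put a number on it. The finding is confined to this mislabelled definition. It does not extend to the assessment window, the primary ORR analysis, the sample size or the error rates.

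**What to change.** Replace the DRR bullet in section 3.2.1.1, Phase II, with wording such as:

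> DRR by RECIST v1.1 is the percentage of subjects with a CR or PR lasting at least 6 months, with duration derived as for DoR (Table 6). It will be estimated as for ORR: point estimate with Clopper-Pearson 95% CI.

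The DCR bullet stays as it is. A note on how responders censored before 6 months are counted would be useful but is optional. Section 3.2.4.1 (no imputation) and section 3.2.14 (denominator of all subjects in the population) already give partial direction, and the choice is the sponsor's.

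The cost is one sentence. Nothing changes in the primary analysis, the Simon design or the listings selected in section 5.

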#### 1.1.2 *Secondary objectives*

##### Phase I

- To determine the whole-body distribution and pharmacokinetics (PK) of  $^{177}\text{Lu}$ -OPS201 after each administration.
- To determine the radiation dosimetry of  $^{177}\text{Lu}$ -OPS201 (organ exposure to radiation) after each administration.
- To determine the PK of OPS201 in plasma and urine.
- To describe the preliminary anti-tumour activity of  $^{177}\text{Lu}$ -OPS201.
- To evaluate progression free survival (PFS) until Long-term Follow-up Visits up to 2 years after the End of Core Trial (EOCT) Visit.
- To determine the uptake of  $^{68}\text{Ga}$ -OPS202 in tumour lesions expressing sstr2 on PET/CT images and estimate its correlation with the uptake on  $^{177}\text{Lu}$ -OPS201 SPECT/CT.
- To evaluate the association between uptake on  $^{68}\text{Ga}$ -OPS202 PET/CT and tumour response to  $^{177}\text{Lu}$ -OPS201.

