##### Phase II

- To evaluate the efficacy of  $^{177}\text{Lu}$ -OPS201 using Response Evaluation Criteria In Solid Tumours (RECIST) v1.1 and/or Positron Emission Tomography Response Criteria In Solid (PERCIST) v1.0 criteria, volumetric CT and modified PERCIST using  $^{68}\text{Ga}$ -OPS202 PET scans and modified RECIST using the  $^{68}\text{Ga}$ -OPS202 avid lesions.
- To evaluate PFS until long-term follow-up visits up to 2 years after the EOCT Visit.
- To estimate the 1-year overall survival (OS) rate.
- To further evaluate the safety profile of  $^{177}\text{Lu}$ -OPS201.
- To evaluate the association between uptake on  $^{68}\text{Ga}$ -OPS202 PET/CT with tumour response to  $^{177}\text{Lu}$ -OPS201 therapy.
- To determine the uptake of  $^{68}\text{Ga}$ -OPS202 in tumour lesions expressing sstr2 on PET/CT images and estimate its correlation with the uptake on  $^{177}\text{Lu}$ -OPS201 SPECT/CT.
- To evaluate the impact of  $^{177}\text{Lu}$ -OPS201 on the health-related quality of life of treated subjects.

SAP Final: Version 2.0: [03 January 2020]

12/57

- To estimate the proportion of sstr2-positive tumour lesions by  $^{68}\text{Ga}$ -OPS202 PET/CT scans as assessed by standardised uptake volume (SUV) in subjects screened for  $^{177}\text{Lu}$ -OPS201 treatment.
- To further assess some PK and dosimetry parameters of  $^{177}\text{Lu}$ -OPS201 based on the phase I results.

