#### *Sstr2 Targeted Tumour Uptake*

Sstr2 targeted tumour uptake will be determined using PET/CT molecular imaging with the companion diagnostic imaging product  $^{68}\text{Ga}$ -OPS202.

The change in  $^{68}\text{Ga}$ -OPS202 PET/CT tumour uptake will be computed as a change in  $\text{SUV}_{\max}$  and  $\text{SUV}_{\text{mean}}$  from baseline to EOCT/EOAC visit. These changes will also be compared to clinical outcome and ORR and to  $^{177}\text{Lu}$ -OPS201 tumour uptake on SPECT/CT.

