SUV max and SUV mean	Screening [a] for  Ga-OPS202 PET/CT; Screening [a] and 6 weeks after second  Lu-OPS201 administration (second cycle)	Uptake on  Ga-OPS202 PET/CT and  Lu-OPS201 therapy response (using ceCT/MRI – RECIST v1.1)	Correlation between the uptake on  Ga-OPS202 PET/CT at baseline [a] with tumour response to  Lu-OPS201 therapy
Lesion count	For  Ga-OPS202 at screening For  Lu-OPS201 at 24 hours after first administration (Cycle 1)	Uptake on  Ga-OPS202-PET/CT and uptake on  Lu-OPS201 SPECT/CT	Correlation between the uptake of  Ga-OPS202 in tumour lesions expressing sstr2 on PET/CT images and the uptake on  Lu-OPS201 SPECT/CT
Identification of avid lesions	Screening [a]	Number of subjects with avid lesions	Proportion of subjects with sstr2-positive tumour lesions by  Ga-OPS202 PET/CT

Abbreviations: ce= Contrast enhanced; CR=Complete response; CT=Computed tomography; DCR=Disease control rate; DoR=Duration of response; DRR=Durable response rate; FDG=Fluorodeoxyglucose; MRI=Magnetic resonance imaging; OS=Overall survival; PERCIST=Positron emission tomography response criteria in solid tumours; PET=Positron emission tomography; PFS=Progression free survival; PR=Partial response; RECIST=Response evaluation criteria in solid tumours; SUL=SUV normalised by lean body mass; SUV=Standardised uptake volume; TTP=Time to progression; TTR=Time to response.

[a] Screening=Baseline scan

Patient Reported Outcomes (PROs) will be assessed in phase II using the following questionnaires: the EuroQoL 5-dimension 5-level (EQ-5D-5L) and European Organization for Research and Treatment of Cancer Quality of Life Questionnaire Core 30 (EORTC QLQ-C30).

The EQ-5D-5L questionnaire is a 2-page, generic preference-based Quality of Life (QoL) measure comprised of a 5-item health status measure and a visual analogue scale and is used to generate two scores. The EQ-5D utility score is based on answers to five questions to evaluate mobility, self-care, usual activities, pain/discomfort and anxiety/depression. Each dimension has 5 levels: no problem, slight problems, moderate problems, severe problems, unable to/extreme.

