#### *1.3.2.7 Nuclear Medicine Imaging for Dosimetry*

All images will be centralised and analysed by independent readers for dosimetry analysis of the dose limiting organs and tumour lesions.

To determine the biokinetics and perform an absolute quantification, whole body scans (planar scintigraphy) and SPECT/CT will be performed at each cycle at the following timepoint ranges just after the end of  $^{177}\text{Lu}$ -OPS201 infusion:

- Day 1: 2 to 4 hours
- Day 2: 16 to 24 hours
- Day 3: 40 to 48 hours
- Day 4 to Day 5: 72 to 96 hours
- Day 6 to Day 7: 144 to 168 hours.

At the timepoint between 16 to 24 hours, SPECT/diagnostic CT will be performed. For all other time points, SPECT/low dose CT will be performed.

For subjects receiving additional administrations (up to four additional cycles), dosimetry assessments will be performed after each additional administration with nuclear medicine imaging described above.

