## **Phase I**

### ***Pharmacokinetics, biodistribution and dosimetry***

For PK, biodistribution and dosimetry of  $^{177}\text{Lu}$ -OPS201, the endpoints are:

- $C_{\max}$ ,  $t_{\max}$ , maximal uptake (%), AUC at the target lesions, discernible organs and blood and elimination half-life ( $t_{1/2}$ ) of radioactivity concentrations in blood.
- Highest absorbed dose, Specific absorbed dose to the target lesions (Gy/GBq), Specific absorbed dose per organ (Gy/GBq) and Cumulative absorbed organ doses (Gy).

For PK of OPS201, the endpoints are:

- Pharmacokinetic parameters including, but not limited to,  $C_{\max}$ , AUC,  $t_{1/2}$ , total plasma clearance (CL), apparent volume of distribution ( $V_d$ ), cumulative amount (of unchanged drug) excreted into the urine ( $A_e$ ), renal clearance, as measured in plasma and urine at defined timepoints.

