- Correlation between change (%) in tumour uptake on  $^{68}\text{Ga}$ -OPS202 (assessed based on SUVmax and SUVmean) PET/CT at baseline with tumour response to  $^{177}\text{Lu}$ -OPS201 therapy using ceCT/MRI RECIST v1.1 will be assessed. Spearman correlation coefficient and its p-value will be reported for change (%) in tumour uptake (assessed based on SUVmax and SUVmean) on  $^{68}\text{Ga}$ -OPS202-PET/CT from Screening and tumor response 6 weeks after second  $^{177}\text{Lu}$ -OPS201 administration (second cycle)
- Correlation between the number of lesion counts from  $^{68}\text{Ga}$ -OPS202 in tumour lesions expressing sstr2 on PET/CT images at screening and the number of lesion counts from  $^{177}\text{Lu}$ -OPS201 SPECT/CT at 24 hours after the first  $^{177}\text{Lu}$ -OPS201 administration (Cycle 1) will be assessed by Pearson correlation coefficient and its p-value.
- Proportion of subjects with sstr2-positive tumour lesions by  $^{68}\text{Ga}$ -OPS202 PET/CT scans as assessed by the identification of avid lesions in subjects screened for  $^{177}\text{Lu}$ -OPS201 treatment at baseline will be summarised and analysed in the same manner as ORR.
- Changes in health-related quality of life scores from baseline to EOCT measured by EQ-5D-5L will be summarised descriptively. Frequency tables will be used to display the number and percentage of subjects of reported problems for each level and each dimension of the EQ-5D-5L by scheduled time point. Shift tables presenting the 2-way frequency tabulation from baseline to the worst post-baseline values will be presented for each dimension of the EQ-5D-5L.
- Changes in health-related quality of life scores (global health status/QoL and each functional scale) from baseline to EOCT measured by EORTC QLQ-C30 will be summarised descriptively.

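### The secondary objective of correlating 68Ga-OPS202 uptake with 177Lu-OPS201 SPECT/CT uptake is analysed only as a Pearson correlation of lesion counts, so the planned statistic does not answer it

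*SAP*

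**What the plan says.** **Objective.** SAP section 1.1.2, Phase I, aims to determine 68Ga-OPS202 uptake in lesions expressing sstr2 "and estimate its correlation with the uptake on" 177Lu-OPS201 SPECT/CT. The Phase II objective has the same content: uptake "in tumour lesions expressing sstr2 on PET/CT images and estimate its correlation with the uptake on" 177Lu-OPS201 SPECT/CT.

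**Endpoint.** Section 3.1.2 repeats uptake against uptake for both phases. The endpoint column of Table 2 does too: 68Ga-OPS202 uptake "in tumour lesions expressing sstr2 on PET/CT images and the uptake on" 177Lu-OPS201 SPECT/CT. Table 1 matches it for Phase I. In both tables the measure in that row is lesion count, taken from PET/CT at screening and from SPECT/CT at 24 hours after the first administration.

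**Analysis.** Section 3.2.1.1, in both phases, specifies "Correlation between the number of lesion counts from" 68Ga-OPS202 PET/CT at screening and the corresponding number on SPECT/CT in Cycle 1. The correlation "will be assessed by Pearson correlation coefficient and its p-value".

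**Other PET-versus-SPECT statements.** Section 1.3.2.1, under Sstr2 Targeted Tumour Uptake, says of the changes in SUVmax and SUVmean: "These changes will also be compared to clinical outcome and ORR and to" 177Lu-OPS201 tumour uptake on SPECT/CT. Section 3.2.1.2 d) plans organ-based and lesion-based sensitivity of PET against SPECT/CT.

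**The concern.** The objective asks whether lesions that take up more of the imaging product also take up more of the therapeutic product. The planned coefficient asks whether subjects with more lesions on one scan have more on the other. Two subjects can have the same pair of counts with entirely different uptake, so the analysis can be carried out exactly as written and leave the objective unanswered.

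The accompanying p-value adds little. It tests for zero linear association between two counts of largely the same lesions, a hypothesis nobody is likely to hold. A near-certain small p-value would then stand under an endpoint worded as an uptake correlation, for a companion diagnostic used to select subjects for treatment.

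**Working it through.** The SAP gives no sample size, power or expected correlation for this endpoint, so there is no figure to reproduce. The check has two parts.

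**1. Tracing the chain in the document**

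| Step | SAP location | Quantity |
|---|---|---|
| Objective | 1.1.2, both phases | uptake v uptake |
| Endpoint | 3.1.2; Tables 1 and 2, endpoint column | uptake v uptake |
| Variable | Tables 1 and 2, variable column | uptake and uptake |
| Measure | Tables 1 and 2, measure column | lesion count |
| Analysis | 3.2.1.1, both phases | lesion count v lesion count, Pearson r and p |

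Elsewhere the SAP does not treat uptake and count as the same thing. It assesses 68Ga-OPS202 uptake by SUVmax and SUVmean in its other uptake endpoints, and section 3.2.3 measures PET/CT uptake by SUVmean. The sentence in section 1.3.2.1 on comparing SUV changes with SPECT/CT uptake names no statistic, and section 3.2.1.1 does not take it up. Section 3.2.1.2 d) yields TP/(TP+FN), which is a detection proportion. No analysis in this SAP relates a PET uptake value to a SPECT/CT uptake value.

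**2. What drives the planned coefficient**

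The document gives no lesion-count distribution or detection rates, so the inputs here are assumptions. Let a subject have N true lesions, with mean m and variance V across subjects. Let PET detect each with probability a and SPECT/CT with probability b, independently given N and unrelated to the size of uptake. Then:

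- covariance of the two counts = a·b·V
- variance of the PET count = a²V + a(1−a)m; for SPECT/CT, b²V + b(1−b)m
- r = √{ [aV / (aV + (1−a)m)] × [bV / (bV + (1−b)m)] }

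Uptake magnitude does not appear. The spread V does: r tends to 1 as V grows relative to m, and r = 0 when V = 0.

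Take N = 2 plus a negative binomial count:

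- overall mean 6, size 2: V = 4 + 4²/2 = 12
- overall mean 10, size 1: V = 8 + 8²/1 = 72

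Worked example with m = 6, V = 12, a = 0.80, b = 0.60: (9.6/10.8) × (7.2/9.6) = 0.889 × 0.750 = 0.667, and √0.667 = 0.82.

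A simulation of 500 runs per scenario, with per-lesion uptake drawn independently on the two scans, gave:

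| Mean lesions | Detection PET/SPECT | r from formula | Mean simulated r (n = 30, 69, 87) |
|---|---|---|---|
| 6 | 0.95 / 0.90 | 0.96 | 0.96, 0.96, 0.96 |
| 6 | 0.90 / 0.80 | 0.92 | 0.91, 0.92, 0.92 |
| 6 | 0.80 / 0.60 | 0.82 | 0.81, 0.81, 0.81 |
| 10 | 0.95 / 0.90 | 0.99 | 0.99, 0.99, 0.99 |
| 10 | 0.90 / 0.80 | 0.98 | 0.97, 0.98, 0.97 |
| 10 | 0.80 / 0.60 | 0.94 | 0.94, 0.94, 0.94 |

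The mean correlation of uptake itself was 0.00 throughout, and the count correlation had p < 0.05 in every run. The sizes n correspond to the Phase I maximum of 30 and the 69 and 87 response-evaluable subjects in Phase II.

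The converse: with exactly 5 lesions in every subject (V = 0) and detection 0.90 and 0.80, the mean count r was between −0.01 and 0.00, however concordant the uptake.

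Association is also not agreement. If PET shows 2, 4, 6, 8, 10, 12 lesions in six subjects and SPECT/CT shows 1, 2, 3, 4, 5, 6, then r = 1.00, although SPECT/CT misses 21 of 42 lesions.

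**The case against.** **The measure is declared.** Tables 1 and 2 name lesion count and the exact scans, section 3.2.1.1 carries this out and labels it a correlation of counts, and a reader of the output would see that. This stands as far as it goes: nothing is substituted covertly, and tables and analysis agree on the measure. It does not resolve the mismatch, because the variable and endpoint in the same table rows are still uptake.

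**Related analyses exist.** The matched detection analysis in section 3.2.1.2 d) covers part of the PET-SPECT relationship. Lesion dosimetry and an integrated model are left to separate plans that are not at hand (sections 3.2.10 and 3.2.11). The first concerns detection only. The others may exist, but this SAP assigns the objective to the count correlation, not to them.

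**Stronger readings that a reader might infer, and that the document does not support:**

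- *That the count carries no information at all on uptake.* A lesion is counted on these scans because it shows visible uptake, so the count is a weak, thresholded proxy.
- *That the coefficient measures agreement in tumour burden.* It measures linear association of lesion numbers, and lesion number is only a proxy for burden.
- *That a single subject can generally set the result.* This applies to Phase I by-cohort results with 3 to 5 subjects. Phase I is also analysed in total, and Phase II by cancer type with far larger numbers.
- *That a misleading coefficient will be reported from this trial.* Section 5 restricts the Clinical Study Report to selected listings after premature closure, and no imaging or correlation output is among them.

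**Choice of method.** A preference for Spearman over Pearson on a descriptive endpoint would be a minor matter by itself. The point rests on the variable analysed, not on the choice of coefficient.

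**Conclusion.** The point holds in a limited form. Followed exactly, the plan would not answer its own secondary objective in either phase, because the only specified PET-SPECT correlation uses lesion numbers. That conclusion comes from the text and needs no assumptions.

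The figures of 0.81 to 0.99 under unrelated uptake are illustrative. They rest on assumed count distributions, assumed detection rates, and detection independent of uptake magnitude. The general result, that between-subject spread in lesion number drives the coefficient, follows from the formula under that last assumption.

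The consequence is small. The endpoint is secondary with no decision attached, ORR and the Simon two-stage design are unaffected, and section 5 reduces the actual report to listings. The correction matters mainly if this text is reused.

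**What to change.** In section 3.2.1.1, both phases, replace the count correlation as the analysis of this endpoint:

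- Use lesions matched by the baseline ceCT/ceMRI mapping already planned in section 3.2.1.2 d), at least the target lesions.
- Correlate screening 68Ga-OPS202 SUVmax and SUVmean with the quantified 177Lu-OPS201 SPECT/CT uptake at 24 hours in Cycle 1.
- Use a rank correlation or a model that allows for several lesions per subject (for example, a bootstrap resampling subjects, or a mixed model), and report the estimate with a confidence interval.
- Keep lesion counts as a separately named detection-concordance summary, shown as the difference in counts per subject.
- Change the measure in the corresponding rows of Tables 1 and 2 to match.

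The inputs are largely planned. Section 1.3.2.7 states the purpose of the scans: "To determine the biokinetics and perform an absolute quantification, whole body scans (planar scintigraphy) and SPECT/CT will be performed at each cycle". It also has tumour lesions read centrally. Section 3.1.2, Phase I, lists maximal uptake and "AUC at the target lesions, discernible organs and blood" as endpoints.

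The cost is modest extra analysis work. The analysis may have to be restricted to target lesions, where quantified uptake is planned. For Phase II, where dosimetry timepoints may be revised after Phase I, quantification of the 24-hour scan would need to be confirmed. If quantified uptake is not wanted, the minimum is to reword the objective and endpoint as lesion-count concordance.
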